7. STATISTICAL METHODS

7.1. Statistical Hypotheses

The primary hypothesis is to evaluate the anticipated drainage (i.e., observed drainage consistent with the patient's clinical presentation) of cerebrospinal fluid (CSF) in the clinical setting until the EVD System is no longer required.

Note: Excessive drainage (e.g., more than 25 cc every hour) not attributable to the patient's condition, widely variable drainage over time inconsistent with the patient's clinical presentation, drainage levels inconsistent with concurrent neurological exams (e.g., GCS, NIHSS, etc.), and/or documented device deficiencies impacting drainage (e.g., breakage disconnection, etc.) are examples of unanticipated drainage of CSF that will be recorded as Adverse Events.

The hypothesis is formulated as

$H_0: P \leq 80\%$ vs. $H_a: P > 80\%$

where P is the proportion of patients with clinical success.

The hypothesis will be evaluated using the exact method along with a two-sided 95% confidence interval. A P-value of less than 0.05 is considered statistically significant.

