	
• EVD system and accessories or procedure related AEs• Noted device deficiencies during use of the EVD system and accessories
Statistical Methods & Analyses:	
Study outcomes will be summarized using descriptive statistics. Categorical variables will be summarized using frequencies and percentages. Continuous variables will be summarized using means, standard deviations, medians, ranges, and numbers of observations.
 
The primary endpoint of success rate will be evaluated against a pre-defined performance goal of 80%. The sample size of 120 patients will provide greater than 80% power to test the hypothesis. A P-value of less than 0.05 is considered statistically significant unless otherwise specified. The secondary endpoint will be summarized descriptively. Subgroup analyses will be performed for drainage systems. Descriptive statistics will be provided for the sub-groups.

Reference:	
Integra's and Codman's External Ventricular Drainage Systems have been on the market for at least 15 years and to date, do not have any unanswered questions on safety or performance. Evidence from peer-reviewed literature has confirmed that these products are safe and perform as intended. The registry design was therefore chosen to capture real-world experience with device use. Integra believes this study design and size is appropriate to confirm the continued safety and performance of these devices given their well-established nature and the existing clinical evidence-base.

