5.5 Primary Study Hypothesis

The primary hypothesis is to evaluate the success rate of CSF drainage against a pre-defined performance goal of 80% (with an expected success rate of 90% or higher). The hypothesis will be tested based on patients of all ages using the exact method along with two-sided 95% confidence interval.

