11.4.3 Analysis of the Primary Endpoint

The primary endpoint of this registry is the anticipated drainage (i.e., observed drainage consistent with the patient's clinical presentation) of cerebrospinal fluid (CSF) in the clinical setting until the EVD System is no longer required.

The number and percentage of patients with anticipated drainage (i.e., observed drainage consistent with the patient's clinical presentation) of cerebrospinal fluid (CSF) in the clinical setting until the EVD System is no longer required will be presented. The primary hypothesis will be tested using the exact (Clopper-

Pearson) method along with two-sided 95% confidence interval. The primary objective will be met if the lower bound of the 95% confidence interval is greater than the performance goal of 80%.

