7.2. Determination of Sample Size

A sample size of 110 is estimated by pre-defined performance goal of 80% along with two-sided 95% confidence interval with 80% power for the primary endpoint. A total of 120 subjects will be enrolled with an 8% potential drop-out assumed. The registry will enroll patients who meet the eligibility criteria with an expected total sample size of 120 patients that underwent the procedure with one or more of the Integra devices at up to 15 study sites. Enrollment will be halted at sites that reach the 34% (40 subjects) inclusion cap. There will be no minimum number of subjects for a single study site.

The device systems have been on the market for more than 15 years and have substantial clinical evidence of safety and performance in the form of several peer-reviewed publications and post-market clinical experience data. In this study, data from multiple centers and nations will be included to ensure that the collected data is from a broad set of surgeons and countries, thereby increasing the generalizability of the outcomes and conclusions.

Integra believes this study design and size is appropriate to confirm the continued safety and performance of these devices given their well-established nature and the existing clinical evidence base.

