8. STATISTICAL ANALYSES

8.1. General Methods

All data collected in this study will be presented using summary tables, figures, and data listings. For categorical data, the number and percentage of subjects in each category will be presented. For continuous data, descriptive statistics, including sample size, mean, median, standard deviation, and range of values (i.e., minimum and maximum values) will be provided.

A significance level of 0.05 will be used for all statistical tests and p-value less than 0.05 will be considered statistically significant unless otherwise specified. The two-sided 95% confidence intervals will be presented whenever appropriate. Statistical analysis will be carried out using SAS software version 9.4 or higher, or other similar validated software.

By-subject listings will be presented for all subjects in the relevant analysis sets.

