8.9.1. Analysis of Primary Endpoint

The primary endpoint is anticipated drainage (i.e., observed drainage consisting with the patient's clinical presentation) of cerebrospinal fluid (CSF) in the clinical setting until the EVD System is no longer required.

Note: Excessive drainage (e.g., more than 25 cc every hour) not attributable to the patient's condition, widely variable drainage over time inconsistent with the patient's clinical presentation, drainage levels inconsistent with concurrent neurological exams (e.g., GCS, NIHSS, etc.), and/or documented device deficiencies impacting drainage (e.g., breakage disconnection, etc.) are examples of unanticipated drainage of CSF that will be recorded as Adverse Events.

The primary hypothesis will be tested using the exact (Clopper-Pearson) method along with two-sided 95% confidence interval. The null hypothesis will be rejected, and primary objective will be met if the lower bound of the 95% confidence interval is greater than the performance goal of 80%.

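### Does leaving the sidedness of the primary P-value unstated in SAP 7.1 put the 80% performance-goal test in doubt?

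*SAP*

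**What the plan says.** SAP 7.1 and protocol 11.1 state the null as a success proportion of 80% or less and the alternative as more than 80%. On the test, SAP 7.1 says "The hypothesis will be evaluated using the exact method along with a two-sided 95% confidence interval", followed by "A P-value of less than 0.05 is considered statistically significant". Protocol 11.1 is worded almost identically. In both places the term two-sided is attached to the interval, and nothing is said about the P-value.

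The decision rule comes later. SAP 8.9.1 names the exact (Clopper-Pearson) method and continues: "The null hypothesis will be rejected, and primary objective will be met if the lower bound of the 95% confidence interval is greater than" the 80% goal. Protocol 11.4.3 agrees: "The primary objective will be met if the lower bound of the 95% confidence interval is greater than the performance goal of 80" percent.

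The sample-size section uses the same interval: "A sample size of 110 is estimated by pre-defined performance goal of 80% along with two-sided 95% confidence interval with 80% power" (SAP 7.2). The expected rate appears only in protocol 5.5: "performance goal of 80% (with an expected success rate of 90% or higher").

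Two general statements of the 0.05 level, in SAP 8.1 ("p-value less than 0.05 will be considered statistically significant unless otherwise specified") and the protocol synopsis ("A P-value of less than 0.05 is considered statistically significant unless otherwise specified"), give way to anything more specific. The sentence in SAP 7.1 and protocol 11.1 carries no such qualifier.

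**The concern.** The natural P-value for a directional alternative is one-sided. Comparing a one-sided P with 0.05 is a 5% test, whereas asking the lower limit of a two-sided 95% interval to clear 80% is a 2.5% test. An analyst who took SAP 7.1 literally and computed a one-sided exact P could report a significant result in a study that had missed its primary objective under SAP 8.9.1.

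This is the only formal hypothesis in an unblinded registry. If the P-value definition were really open, it could be chosen after the results were known. The sentence in SAP 7.1 is also written for this hypothesis and has no escape clause, so it cannot be set aside as a general default.

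**Working it through.** **Inputs.** Goal p0 = 0.80 (SAP 7.1); expected rate p1 = 0.90 (protocol 5.5); 110 evaluable, 120 enrolled, 8% drop-out, 80% power (SAP 7.2); success rule from SAP 8.9.1.

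**1. Which significance level gives the plan's 110?** Normal approximation for one proportion:

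n = [(z_α·√(p0·(1−p0)) + z_β·√(p1·(1−p1))) / (p1 − p0)]², with √(0.8×0.2) = 0.4, √(0.9×0.1) = 0.3 and z_β = 0.8416.

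- One-sided 0.025: [(1.960×0.4 + 0.8416×0.3)/0.1]² = 107.4, so 108.
- One-sided 0.05: [(1.645×0.4 + 0.8416×0.3)/0.1]² = 82.9, so 83.

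The stated 110 is close to 108 and far from 83. Exact power at a true 90% under the lower-limit rule is 79.1% at n = 110 and 85.6% at n = 120. Under one-sided P < 0.05 it would be 86.6% and 91.0%. For drop-out, 110/(1 − 0.08) = 119.6, so 120. The design rests on the 0.025 rule.

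**2. Where would the two readings disagree?** The Clopper-Pearson lower limit for x successes exceeds 0.80 exactly when P(X ≥ x | n, 0.80) < 0.025. Counts around the cut-off:

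| Successes | One-sided P | Doubled-tail P | 95% lower limit | SAP 8.9.1 met? |
|---|---|---|---|---|
| 95/110 | 0.0559 | 0.1119 | 78.51% | no |
| 96/110 | 0.0320 | 0.0640 | 79.57% | no |
| 97/110 | 0.0170 | 0.0340 | 80.64% | yes |
| 103/120 | 0.0647 | 0.1295 | 78.29% | no |
| 104/120 | 0.0388 | 0.0775 | 79.25% | no |
| 105/120 | 0.0218 | 0.0436 | 80.22% | yes |

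A one-sided P against 0.05 disagrees with the rule at one count at each planned size, 96/110 and 104/120. The doubled-tail P against 0.05 agrees in every row. It must, since 2P < 0.05 is the same condition as P < 0.025.

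**3. How likely is the discordant count?**

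| True success rate | n = 110 | n = 120 |
|---|---|---|
| 80% | 1.5% | 1.7% |
| 85% | 9.0% | 9.3% |
| 90% | 7.4% | 5.4% |
| 95% | 0.08% | 0.02% |

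These are chances of a mismatched label, and only if P is reported one-sided against 0.05. They are not chances of a wrong decision.

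**4. Error rate of the stated rule.** At a true rate of 80%, P(X ≥ 97 | 110) = 1.70% and P(X ≥ 105 | 120) = 2.18%, both below 2.5%.

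**The case for a change.** The case for amending the plan is that the hypothesis is directional, the 0.05 sentence is specific to it and unqualified, and one clarifying sentence in the SAP would close the matter. Calling P two-sided might not be enough either, because exact two-sided P-values have more than one definition. The minimum-likelihood version can part from the Clopper-Pearson limit at some sizes: 98/112 gives P = 0.045 with a lower limit of 79.9%. The final number analysed is not fixed in advance.

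What stands is that the sidedness is not written down and that a one-sided reading produces the conflicts shown. The rest has little force. No section makes P < 0.05 a separate route to success. The sentence just before it in SAP 7.1 pairs the exact method with a two-sided 95% interval, of which 0.05 is the complement. A directional alternative judged by a two-sided 95% limit is an ordinary pairing, and it is the one SAP 8.9.1 spells out. The minimum-likelihood P is not mentioned anywhere. The plan names Clopper-Pearson, an equal-tailed method whose matching two-sided P is the doubled tail, and with that P there is no conflict at any n from 105 to 120.

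**Conclusion.** No change follows. The plan leaves a descriptive detail unstated, but the inferential rule is complete: SAP 8.9.1 says when the null is rejected, protocol 11.4.3 says when the objective is met, and they use the same limit. The sample size was built on that limit. An analyst who reads these sections together will report the doubled-tail exact P against 0.05, or equivalently the one-sided P against 0.025, beside the interval.

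The most that could go wrong is a P of 0.032 or 0.039 labelled significant beside a lower limit of 79.6% or 79.3%, at one count per planned size. If the true rate is 90%, that count has a probability of 7.4% (n = 110) or 5.4% (n = 120). Even then the objective would be unmet under the stated rule, with the interval there to show it. Success would still need 97 of 110 or 105 of 120, and error rate, power and sample size would be untouched.

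This rests on treating SAP 8.9.1 as the governing rule, as its wording does, and on the 90% expected rate from protocol 5.5 for the power and probability figures.

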7.2. Determination of Sample Size

A sample size of 110 is estimated by pre-defined performance goal of 80% along with two-sided 95% confidence interval with 80% power for the primary endpoint. A total of 120 subjects will be enrolled with an 8% potential drop-out assumed. The registry will enroll patients who meet the eligibility criteria with an expected total sample size of 120 patients that underwent the procedure with one or more of the Integra devices at up to 15 study sites. Enrollment will be halted at sites that reach the 34% (40 subjects) inclusion cap. There will be no minimum number of subjects for a single study site.

The device systems have been on the market for more than 15 years and have substantial clinical evidence of safety and performance in the form of several peer-reviewed publications and post-market clinical experience data. In this study, data from multiple centers and nations will be included to ensure that the collected data is from a broad set of surgeons and countries, thereby increasing the generalizability of the outcomes and conclusions.

Integra believes this study design and size is appropriate to confirm the continued safety and performance of these devices given their well-established nature and the existing clinical evidence base.

7.3. Analysis Populations

The Intent to Treat (ITT) population consists of all patients who signed the written informed consent and are considered to meet all inclusion/exclusion criteria (patients included in the study) following the Intention to Treat principle whether patients have or not a procedure with one of the Integra or Codman External Ventricular Drainage System.

The Full Analysis Set (FAS) population consists of all patients included in the study who have a procedure with one of the Integra or Codman External Ventricular Drainage System.

The Per Protocol Set (PPS) population consists of all patients who have a procedure with one of the Integra or Codman External Ventricular Drainage System and meet all inclusion/exclusion criteria, and without major protocol deviation during the study. Primary and secondary endpoints analyses based on the PPS population will be supportive.

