10 PATIENT DISCONTINUATION OF CONSENT FOR THE STUDY

IMPORTANT: This section is only applicable to sites and/or patients who have consented to have their data collected as part of this registry.

Patient participation in the registry study is considered complete when the EVD System is no longer required for drainage and monitoring of CSF. The registry study is considered complete upon the EVD System is no longer required for drainage and monitoring of CSF of the last patient.

A patient may withdraw consent for data to be collected in the registry study at any time during the registry study. The patient does not have to give a reason for withdrawal of consent. The investigator may exclude a patient if the patient or the patient's data does not fulfil the eligibility criteria (**Section 6.1-6.2**). The investigator may also decide to stop collecting a patient's data for the registry study if the investigator feels it is in the patient's best interest.

The Sponsor or its representative shall be notified immediately when a patient's consent is withdrawn or discontinued for any reason. Premature registry study end date and reason (if known) shall be documented on the CRF.

The data collected up to the date the patient has withdrawn consent will be included as part of the registry study results, as permitted by national laws and regulations. Additional safety information may be requested from a withdrawn or discontinued patient if it is considered clinically relevant.

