11.3 Populations for Analyses

The Intent to Treat (ITT) population consists of all patients who signed the written informed consent and are considered to meet all inclusion/exclusion criteria (patients included in the study) following the Intention To Treat principle whether patients have or not a procedure with one of the Integra or Codman External Ventricular Drainage System.

The Full Analysis Set (FAS) population consists of all patients included in the study who have a procedure with one of the Integra or Codman External Ventricular Drainage System. The primary endpoint and all other endpoints analyses will be based on the FAS population.

The Per Protocol Set (PPS) population consists of all patients who have a procedure with one of the Integra or Codman External Ventricular Drainage System and meet all inclusion/exclusion criteria. Endpoints analyses based on the PPS population will be supportive.

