12.1.9 Protocol Deviations

A protocol deviation is an instance of failure to follow, intentionally or unintentionally, the requirements of the protocol (ISO 14155 Definition). The investigator is not allowed to deviate from the protocol without first receiving approval in writing from the Sponsor, involved EC, and applicable regulatory authorities. Deviations from the protocol to protect the rights, safety, and well-being of human subjects under emergency circumstances or situations beyond the investigator's control (such as subjects not attending scheduled follow-up visits, etc. may proceed without prior approval of the sponsor and the EC.

Approval for deviations shall be documented in writing and maintained in the investigator and clinical investigation files.

The use of waivers from the protocol is prohibited.

A Major Protocol Deviation is defined as an event that resulted in an increased risk to a subject or others; affected the right, safety, or welfare of a subject; or affected the scientific integrity of the clinical investigation. Major Protocol Deviations might include, but are not limited to, the following list:

- Failure to obtain informed consent prior to subject enrollment
- Enrolled subject did not meet the inclusion/exclusion criteria
- Impacts subject safety or alters risks to subjects

Any other events or omissions that do not comply with the requirements of the protocol will be considered Minor Protocol Deviations. Minor Protocol Deviations might include, but are not limited to, the following list:

- Incorrect version of the informed consent form used.
- Follow-up visit was outside the required window.

All Major Protocol Deviations from the protocol must be reported promptly, but in no event later than 5 business days, to the appointed Sponsor representative/clinical investigation monitor via e-mail, regardless of whether they were medically justifiable, pre-approved by the Sponsor or taken to protect the subject in an emergency. In addition, Investigators will also adhere to procedures for reporting deviations to the involved EC in accordance with their specific reporting policies and procedures.

As a result of deviations, corrective actions are to be developed by the site and implemented promptly.

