8.10. Safety Analyses

All safety summaries will be presented for the FAS population. No formal statistical testing is planned on safety endpoints.

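### The FAS rests on an eligibility judgement with no fixed time point, so it is unclear whether a treated patient later judged ineligible stays in the primary analysis and the safety tables

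*SAP*

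**What the plan says.** **Analysis sets.** In SAP 7.3 (Protocol 11.3 reads alike), the ITT set is consented patients who "are considered to meet all inclusion/exclusion criteria (patients included in the study"; the phrase in brackets serves as the definition of an included patient. The FAS then "consists of all patients included in the study who have a procedure with one of the Integra or Codman" system. In the protocol, the Per Protocol Set (PPS) is patients who had a procedure "and meet all inclusion/exclusion criteria. Endpoints analyses based on the PPS population will be supportive". The SAP's PPS also requires the absence of a major deviation.

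**Use of the sets.** Protocol 11.3 and SAP 8.9 put the primary analysis on the FAS. SAP 8.10 states: "All safety summaries will be presented for the FAS population". There is no separate safety set of all treated patients.

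**Exclusion and timing.** Protocol section 10 lets the investigator exclude a patient when the patient or the patient's "data does not fulfil the eligibility criteria". It gives no cut-off, and its rule on keeping data is written for withdrawal of consent. Protocol 6.3 screens patients after consent and accepts consent after drainage has ended. Protocol 11.4.2 states that there is no blinding. Exclusion criteria 5 and 7 in Protocol 6.2 rest on the investigator's judgement.

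**Text pointing the other way.** Protocol 12.1.9 lists as a major deviation: "Enrolled subject did not meet the inclusion/exclusion criteria".

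**The concern.** An analysis set in a single-arm, unblinded study should not depend on a judgement that can be made or revised once the outcome is known. Here the set depends on being considered eligible, the plan does not say at what moment, and for patients consented after drainage has ended the result is already in the chart when they are screened. A chart may well be looked at harder when drainage failed or a complication occurred. If that leads to exclusion, failures leave the denominator more often than successes do. The success rate tested against 80% is then too high and the tabulated adverse event rate too low, in a registry meant to confirm both performance and safety.

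On the reading in which such patients leave the FAS, no planned analysis shows the effect. The ITT set carries the same eligibility condition, the protocol's PPS is nearly the same set as its FAS, and the SAP's PPS only removes more patients.

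**Working it through.** **1. The two readings side by side**

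| Text | Eligibility judgement stays open | Eligibility judged once, at inclusion |
|---|---|---|
| ITT and FAS wording (Protocol 11.3, SAP 7.3) | Patient no longer considered eligible, so outside ITT and FAS | Patient was considered eligible when included, so stays |
| PPS eligibility clause | Adds almost nothing to the protocol's FAS | Does real work: removes patients later found ineligible |
| Major deviation for an ineligible enrolled subject (Protocol 12.1.9) | Fits poorly | Fits: the subject remains enrolled and leaves the SAP's PPS |
| Investigator exclusion (Protocol section 10) | Fits: the patient is taken out | Unclear: nothing says the data stay |

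Neither column fits every passage.

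**2. The plan's own sample size**

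Inputs: performance goal 80% and expected rate 90% (Protocol 5.5); 110 evaluable, 80% power, 8% drop-out, 120 enrolled (Protocol 11.2, SAP 7.2). SAP 7.1 says "A P-value of less than 0.05 is considered statistically significant". SAP 8.9.1 gives the operative rule: the "primary objective will be met if the lower bound of the 95% confidence interval is greater than the performance goal of 80" per cent. That rule has a one-sided level of at most 2.5%.

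The exact (Clopper-Pearson) lower bound for x successes in n is L(x, n) = the 0.025 quantile of Beta(x, n − x + 1).

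- L(97, 110) = 0.8064 passes and L(96, 110) = 0.7957 fails, so 97 successes are needed.
- Power at 90%: P(X ≥ 97 | 110, 0.90) = 79.1%, close to the stated 80%.
- Type I error at 80%: P(X ≥ 97 | 110, 0.80) = 1.7%.
- Drop-out: 110 / (1 − 0.08) = 119.6, rounded up to 120.

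The sample size reproduces and is not in dispute.

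**3. How few exclusions change the result**

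| All treated | Lower bound | Failures removed | Analysed | Lower bound |
|---|---|---|---|---|
| 96/110 | 79.6%, fails | 1 | 96/109 | 80.5%, passes |
| 95/110 | 78.5%, fails | 2 | 95/108 | 80.3%, passes |
| 94/110 | 77.5%, fails | 3 | 94/107 | 80.1%, passes |

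The margin is the same at 120: 104/120 fails (79.3%) and 104/119 passes (80.1%).

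**4. Effect on type I error**

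The documents give no expected number of ineligible patients, so the exclusion fraction q is an assumption. Let each failure be removed independently with probability q and no success be removed. With a true rate of 80% and N treated:

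P(pass) = Σₓ Bin(x; N, 0.80) · Σⱼ Bin(j; N − x, q) · 1[L(x, N − j) > 0.80]

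| q | N = 110 | N = 120 |
|---|---|---|
| 0 | 1.7% | 2.2% |
| 5% | 3.0% | 3.3% |
| 10% | 4.9% | 4.8% |
| 20% | 10.4% | 11.5% |

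This is a one-sided worst case. Exclusion unrelated to outcome keeps the exact test at or below 2.5%.

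**The case against.** The strongest answer is that the ITT and FAS wording refers to patients considered eligible, while only the PPS requires that they meet the criteria. Read that way, the FAS rests on the judgement at inclusion and the PPS on verified eligibility, and a patient found ineligible later leaves the PPS alone. Protocol 12.1.9 and the otherwise redundant PPS clause support this. It may well be what the authors intended, but section 10 does not say so and no passage fixes the time of the judgement.

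A reader might also infer more than the documents support:

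- *That the FAS plainly holds only verified-eligible patients.* The word considered leaves this open.
- *That the investigator may exclude at any time.* In section 10 that freedom is given to the patient withdrawing consent. On the timing of investigator exclusion the text is silent, which is a gap and not a permission.
- *That coagulopathy discovered after a hemorrhage makes the patient ineligible.* Exclusion criterion 8 concerns coagulopathy that is known, so this is a poor example.
- *That the data-availability criterion is a general way out.* Inclusion criterion 3 applies only where the system was removed before enrolment.
- *That adverse events vanish.* Protocol 9.7 collects them on all subjects. SAP 8.2.1 tabulates and lists discontinuations with reasons, and SAP 8.2.2 lists deviations. Exclusions would be visible. The possible loss is from the primary analysis and the FAS tables, and disposition counts do not show the excluded patients' drainage outcome.

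Finally, nothing in the documents says that selective exclusion will happen.

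**Conclusion.** The point holds as an ambiguity that needs resolving before analysis. The plan does not fix when eligibility for the FAS is judged or say what happens to the data of a treated patient excluded on eligibility, and Protocol sections 10, 11.3 and 12.1.9 and SAP 7.3 do not agree. It cannot be said that the plan removes these patients; it can be said that the plan does not ensure they stay.

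The one-patient margin (96/110 against 96/109) follows from the stated rule and needs no assumption beyond 110 treated patients. The rise in type I error from 1.7% to between 3.0% and 10.4% rests on assumed exclusion fractions of 5% to 20%, applied to failures only. The change should be made: it costs little, and a single disputed exclusion could decide the primary conclusion.

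**What to change.** - **Protocol 11.3 and SAP 7.3:** define the FAS as all consented patients (own consent or by representative) who passed screening and in whom a procedure with an Integra or Codman EVD System was started, regardless of any later eligibility finding. Use it for the primary endpoint and all safety summaries. The screening condition keeps out the screen failures of Protocol 6.5, for whom 6.3 does not foresee data collection.
- **PPS:** let later eligibility findings remove patients from this set only, and log each as a major deviation under 12.1.9.
- **Protocol section 10:** state that exclusion on eligibility after enrolment removes neither the patient nor the data already collected from the FAS.
- **Patients consented after implant:** judge eligibility only on facts documented as known before implant, plus the data-availability check in inclusion criterion 3. A cut-off tied to data entry would not be enough, because for some of these patients the outcome is known before any entry is made.
- **Reporting:** give the number of, and reasons for, all post-consent screen failures.

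The cost is a wording change in both documents and one reporting line, with no added patients or assessments. Success and adverse event rates may come out slightly less favourable.
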